#### **10.2.7.2 Fasciculations**

Fasciculations will also be recorded in the daily diary. At Baseline, Weeks 4, 6, 8 and 12, subjects will be asked several questions related to their fasciculations experienced in the previous 14 days. Reference the study Manual of Procedures for additional information.

For the purpose of this study, a fasciculation is a brief, spontaneous contraction affecting a small number of muscle fibers, often causing a flicker of movement under the skin. Defining interference with daily activities may be different for each subject and defining daily activities will be different for each subject.

## 11 SAFETY AND ADVERSE EVENTS

The AE definitions and reporting procedures provided in this protocol comply with all applicable International Conference on Harmonization (ICH) guidelines. The SI will carefully monitor each subject throughout the study for possible AEs. All AEs will be documented on CRFs designed specifically for this purpose. It is also important to report all AEs, especially those that result in permanent discontinuation of the investigational product being studied, whether serious or non-serious.

### 11.1 Definitions of AEs, Suspected Adverse Drug Reactions & SAEs

#### 11.1.1 Adverse Event and Suspected Adverse Drug Reactions

An AE is any unfavorable and unintended sign (including a clinically significant abnormal laboratory finding, for example), symptom, or disease temporally associated with a study, use of a drug product or device whether or not considered related to the drug product or device.

Adverse drug reactions (ADR) are all noxious and unintended responses to a medicinal product related to any dose. The phrase “responses to a medicinal product” means that a causal relationship between a medicinal product and an AE is at least a reasonable possibility, i.e., the relationship cannot be ruled out. Therefore, a subset of AEs can be classified as suspected ADRs, if there is a causal relationship to the medicinal product.

Examples of AEs include: new conditions, worsening of pre-existing conditions, clinically significant abnormal physical examination signs (e.g., skin rash, peripheral edema), or clinically significant abnormal test results (e.g., lab values or vital signs), with the exception of outcome measure results, which are not being recorded as AEs in this trial (they are being collected, but analyzed separately). Stable chronic conditions (e.g., diabetes, arthritis) that are present prior to the start of the study and do not worsen during the trial are NOT considered AEs. Chronic conditions that occur more frequently (for intermittent conditions) or with greater severity, would be considered as worsened and therefore would be recorded as AEs.

AEs are generally detected in two ways:

Clinical → symptoms reported by the subject or signs detected on examination.

Ancillary Tests → abnormalities of vital signs, laboratory tests, and other diagnostic procedures (other than the outcome measures, the results of which are not being captured as AEs).

For the purposes of this study, symptoms of progression/worsening of ALS, including ‘normal’ progression, will be recorded as AEs.

The following measures of disease progression will not be recorded as AEs even if they worsen (they are being recorded and analyzed separately): vital capacity results and ALSFRS-R results.

If discernible at the time of completing the AE log, a specific disease or syndrome rather than individual associated signs and symptoms should be identified by the SI and recorded on the AE log. However, if an observed or reported sign, symptom, or clinically significant laboratory anomaly is not considered by the SI to be a component of a specific disease or syndrome, then it should be recorded as a separate AE on the AE log. Clinically significant laboratory abnormalities, such as those that require intervention, are those that are identified as such by the SI.

Subjects will be monitored for AEs from the time they sign consent until completion of their participation in the study (defined as death, consent withdrawal, loss to follow up, early study termination for other reasons or following completion of the entire study).

An unexpected AE is any AE, the specificity or severity of which is not consistent with the current IB. An unexpected, suspected ADR is any unexpected AE that, in the opinion of the SI or Sponsor, there is a reasonable possibility that the investigational product caused the event.

#### **11.1.1.1 Adverse Events of Special Interest**

All subjects participating in this trial will be informed that they could be at risk for:

- new or worsened urinary retention (in the clinical judgment of the site investigator)
- retinal hyperpigmentation abnormalities and/or vision loss,
- pigmentation of non-retinal ocular tissues (e.g., conjunctiva, sclera, iris)
- discoloration of nails, lips, skin (including skin around the eyes) or mucosa.

Subjects must inform the SI of any of these symptoms immediately. The SI must contact the Medical Monitor to discuss the subject’s continued use of study drug. Per the discretion of the SI, subjects may be referred to a dermatologist for skin discoloration at any point in the study.

Special attention must also be made for AEs of possible drug-induced liver injury with hyperbilirubinemia defined as ALT 3x ULN and bilirubin 2x ULN (with >35% direct).

#### **11.1.2 Serious Adverse Events**

An SAE is defined as an AE that meets any of the following criteria:

1. Results in death.
2. Is life threatening: that is, poses an immediate risk of death as the event occurred.

- a. This serious criterion applies if the study subject, in the view of the SI or Sponsor, is at immediate risk of death from the AE as it occurs. It does not apply if an AE hypothetically might have caused death if it were more severe.
3. Requires inpatient hospitalization for 24 hours or more or prolongation of existing hospitalization.
  - a. Hospitalization for an elective procedure (including elective PEG tube/g-tube/feeding tube placement) or a routinely scheduled treatment is not an SAE by this criterion because an elective or scheduled “procedure” or a “treatment” is not an untoward medical occurrence.
4. Results in persistent or significant disability or incapacity.
  - a. This serious criterion applies if the “disability” caused by the reported AE results in a substantial disruption of the subject’s ability to carry out normal life functions.
5. Results in congenital anomaly or birth defect in the offspring of the subject (whether the subject is male or female).
6. Necessitates medical or surgical intervention to preclude permanent impairment of a body function or permanent damage to a body structure.
7. Important medical events that may not result in death, are not life-threatening, or do not require hospitalization may also be considered SAEs when, based upon appropriate medical judgment, they may jeopardize the subject and may require medical or surgical intervention to prevent one of the outcomes listed in this definition. Examples of such medical events include blood dyscrasias or convulsions that do not result in inpatient hospitalization, or the development of drug dependency or drug abuse.

An inpatient hospital admission in the absence of a precipitating, treatment-emergent, clinical AE may meet criteria for "seriousness" but is not an adverse experience, and will therefore, not be considered an SAE. An example of this would include a social admission (subject admitted for other reasons than medical, e.g., lives far from the hospital, has no place to sleep).

A serious, suspected ADR is an SAE for which, in the opinion of the SI or Sponsor, there is a reasonable possibility that the investigational product caused the event.

The SI is responsible for classifying AEs as serious or non-serious.

## **11.2 Assessment and Recording of Adverse Events**

The SI will carefully monitor each subject throughout the study for possible AEs. All AEs will be documented on CRFs designed specifically for this purpose. All AEs will be collected and reported in the EDC system and compiled into reports for monthly reviewing by the Medical Monitor. The Medical Monitor shall promptly review all information relevant to the safety of the investigational product, including all SAEs. Special attention will be paid to those that result in

permanent discontinuation of the investigational product being studied, whether serious or non-serious.

### **11.2.1 Assessment of Adverse Events**

At each visit (including telephone interviews), the subject will be asked if they have had any problems or symptoms since their last visit in order to determine the occurrence of AEs. If the subject reports an AE, the SI will probe further to determine:

1. Type of event
2. Date of onset and resolution (duration)
3. Severity (mild, moderate, severe)
4. Seriousness (does the event meet the above definition for an SAE)
5. Causality, relation to investigational product and disease
6. Action taken regarding investigational product
7. Outcome

### **11.2.2 Relatedness of Adverse Event to Investigational Product**

The relationship of the AE to the investigational product should be specified by the SI using the following definitions:

1. Not Related: Concomitant illness, accident or event with no reasonable association with treatment.
2. Unlikely: The reaction has little or no temporal sequence from administration of the investigational product, or a more likely alternative etiology exists.
3. Possibly Related: The reaction follows a reasonably temporal sequence from administration of the investigational product and follows a known response pattern to the suspected investigational product; the reaction could have been produced by the investigational product or could have been produced by the subject's clinical state or by other modes of therapy administered to the subject. (Suspected ADR)
4. Probably Related: The reaction follows a reasonably temporal sequence from administration of investigational product; is confirmed by discontinuation of the investigational product or by re-challenge; and cannot be reasonably explained by the known characteristics of the subject's clinical state. (Suspected ADR)

5. Definitely Related: The reaction follows a reasonable temporal sequence from administration of investigational product; that follows a known or expected response pattern to the investigational product; and that is confirmed by improvement on stopping or reducing the dosage of the investigational product, and reappearance of the reaction on repeated exposure (Suspected ADR).

### 11.2.3 Recording of Adverse Events

All clinical AEs are recorded in the AE Log in the subject's study binder. The site should fill out the AE Log and enter the AE information into the EDC system within 48 hours of the site learning of a new AE or receiving an update on an existing AE.

**Please Note:** SAEs must be reported to the NCRI CC within 24 hours of the site learning of the SAE. This applies regardless of whether the subject is taking study drug or not. Any events of drug-induced liver injury, retinal pigmentation and/or vision loss, skin pigmentation changes or urinary retention, whether classified as SAEs or not, must also be reported within 24 hours.

Entries on the AE Log (and into the EDC) will include the following: name and severity of the event, the date of onset, the date of resolution, relationship to investigational product, action taken, and primary outcome of event.

### 11.3 Adverse Events and Serious Adverse Events - Reportable Events

The following are considered reportable events and must be reported to the NCRI CC within 24 hours of the site being notified of the event.

- All events that meet the above criteria for Serious Adverse Events (SAEs)
- Events of special interest as described in Section 11.1.1.1.
- Dosage Changes (Dose Management)
  - Investigational Product Suspension, Reduction or Re-challenge
  - Investigational Product Discontinuation
- Key Study Events:
  - Subject Final Disposition
  - Feeding Tube Placement
  - Permanent Assisted Ventilation (PAV)\*
  - Tracheostomy
  - Mortality
  - Pregnancy

- Diaphragm Pacing System (DPS) device implantation

\* Permanent Assisted Ventilation (PAV) is defined as more than 22 hours daily of non-invasive mechanical ventilation for more than one week. The date of onset of PAV is the first day of the seven days.

## **12 DATA SAFETY MONITORING**

### **12.1 Data and Safety Monitoring Board**

An independent DSMB will be assembled for the trial. The DSMB receives the blinded and unblinded summary reports of the frequency of all clinical AEs and safety laboratory tests for planned periodic meetings approximately every 3-6 months throughout the study. Meetings will be held via teleconference. In addition, the DSMB Chair may call ad hoc meetings.

Summaries of SAEs and enrollment will be provided approximately monthly to the DSMB by the Study Biostatistician. AEs occurring within 24 hours of dosing, AE(s) related to visual acuity, skin pigmentation, hyperbilirubinemia, and urinary retention, and any severe unexpected SAEs are considered events of interest and will be reported in the monthly summaries to the DSMB by the NCRI CC. The DSMB can ask to receive the SAE reports more frequently. As necessary, the DSMB can review the frequencies of clinical and laboratory abnormalities. Recommendations for modification or termination of the trial based on safety data will be made by the DSMB to the PI and Steering Committee. The DSMB will review safety data throughout the trial and may stop the trial for safety if it determines that there is a significant difference in the rate of a particular AE that would indicate a risk that is greater than the possible benefit of the study drug. A notable increase in the frequency of any AE should be examined by the DSMB although it may not lead to a recommendation by the DSMB. There will not be early stopping for efficacy in this trial.

Prior to each DSMB meeting, the NCRI CC will provide an update to the DSMB on enrollment, data quality (missing data) and protocol adherence. The NCRI CC will be responsible for communication with the DSMB.

Complete information can be found in the Data and Safety Monitoring Plan.

### **12.2 Safety Monitoring**

#### **12.2.1 Safety Management Resource Team**

The NCRI CC Safety Management Resource Team (SMaRT) is comprised of physicians, project managers, data managers, and systems personnel. On a periodic basis, the SMaRT will review AEs, SAEs, abnormal laboratory measurements, ECGs and protocol deviations as detailed in the study's Safety Management Plan.

### **12.2.2 Medical Monitoring**

The designated Medical Monitor for the study is identified in the Site Manual of Procedures. Site personnel should contact the Medical Monitor for assistance with the following:

- Medically-related protocol questions
- Safety concerns, including AEs and SAEs
- Protocol deviations
- Protocol eligibility questions

The Medical Monitor can decide whether a specific subject must discontinue study drug due to concerns about recurrent or persistent serious side effects such as cardiac events.

## 13 STATISTICAL CONSIDERATIONS

### 13.1 Analysis Populations

The unmatched healthy controls, matched healthy controls, and ALS subjects represent three distinct populations of individuals for the purposes of analysis. Some unmatched or matched healthy controls may be excluded from analysis if there is good reason to question their status as neurologically normal. All ALS subjects who are randomized and receive at least one dose of study drug will compose the modified intention to treat (mITT) population and will be included in primary analyses of safety, tolerability, and efficacy. For mITT analyses, subjects will be grouped according to their randomized treatment assignment regardless of treatment actually received or compliance with assigned treatment.

### 13.2 Analysis of Unmatched Healthy Control Subjects

Neurophysiological testing (TMS and NCS) will be performed on unmatched healthy control subjects at each site to evaluate test-retest variation of the primary outcome prior to activating a site for enrollment of ALS subjects. Approximately five unmatched healthy control subjects per site will each undergo three repeat neurophysiological testing sessions. The Steering Committee will review estimates of test-retest reliability and other measures of site performance dynamically and will determine when individual sites may begin enrolling ALS subjects. The Steering Committee may adjust the number of healthy controls and the number of testing sessions per subject at individual sites based on the existing data at the time of review. The decision to activate a site to enroll ALS subjects will take into consideration the test-retest variation relative to performance at other participating sites. The goal will be to activate eight (8) to twelve (12) sites to recruit ALS subjects. The Steering Committee may recommend additional healthy control testing and delayed activation of sites to recruit ALS subjects.

Estimates of test-retest variability will be obtained by analysis of the unmatched healthy control subjects using random effects models with random intercepts for site and subject and site-specific within-person heteroscedasticity,

$$Y = \mu + a_i + b_{ij} + \epsilon_{ijk}$$

where  $i$  indexes site,  $j$  indexes subject, and  $k$  indexes repeated testing sessions,  $a_i \sim N(0, \text{Var}[a])$ ,  $b_{ij} \sim N(0, \text{Var}[b])$ , and  $\epsilon_{ijk} \sim N(0, \text{Var}[\epsilon]_i)$ . Test-retest reliability will be calculated as the person-level intraclass correlation, the ratio of among-person variance over the sum of among-person and within-person variance for a given site. By assuming that among-person variance is not site-specific, a site can achieve high intraclass correlation only by ensuring low within-person variance, not by enrolling highly variable subjects. TMS and NCS parameters will be analyzed on their original scale or after log transformation depending on which scale yields residuals that

are more nearly normally distributed by the Anderson-Darling goodness of fit statistic. The Steering Committee may also consider the absolute magnitudes of TMS and NCS parameter estimates for each site in evaluating site performance.

### 13.3 Primary Analysis

We will test the effect of ezogabine on SICI using the mITT sample of ALS subjects in a shared-baseline mixed model with fixed effects for visit (6 levels: Screening, Baseline, and Weeks 4, 6, 8, and 12), treatment group (3 levels: placebo and 600 and 900 mg/day ezogabine) x post-baseline visit (4 levels) and random site-specific intercepts and random participant-specific intercepts and slopes with unstructured covariance. The use of a shared-baseline reflects the homogeneity of the trial cohort prior to randomization and the combination with participant-specific random effects induces an adjustment for any chance baseline differences similar to ANCOVA (Liu et al, 2009). We will use linear contrasts to test for dose-dependent differences in change from baseline to the average SICI over the stable dose period from weeks 6 through 8. A significant reduction of SICI (i.e., higher MEP amplitude) of either dose relative to placebo would be accepted as evidence of benefit from ezogabine treatment.

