# SCHEDULE OF ACTIVITIES (ALS SUBJECTS)

Activity	Screening Visit	Baseline Visit 	Week 2 Call	Week 4 Visit 	Week 6 Visit 	Week 8 Visit 	Week 10 Call	Week 12 Visit	Week 14 Call
	CLINIC	CLINIC	CALL	CLINIC	CLINIC	CLINIC	CALL	CLINIC	CALL
	-21 days	Day 0	Day 14 ± 3	Day 28 ± 3	Day 42 ± 3	Day 56 ± 3	Day 70 ± 3	Day 84 ± 3	Day 98 +5
Written Informed Consent	X								
Inclusion/Exclusion Review	X								
Medical History	X								
Demographics	X								
ALS Diagnosis History	X								
Concomitant Medication Review	X	X	X	X	X	X	X	X	X
Adverse Event Review 	X	X	X	X	X	X	X	X	X
Physical Examination	X							X	
Neurological Exam	X							X	
Manual Muscle Testing (MMT)	X							X	
Vital Signs 	X	X		X	X	X		X	
12-Lead Electrocardiogram (ECG)	X	X 			X			X	
Height & Weight 	X	X		X	X	X		X	
Safety Labs 	X			X	X	X		X	
Urological Symptom Score	X			X		X		X	
ALSFRS-R	X	X		X	X	X		X	
Slow Vital Capacity (SVC)	X	X		X	X	X		X	
Hand Held Dynamometry (APB only)	X	X		X	X	X		X	
Assign Global Unique Identifier (GUID)	X								
Blindedness Questionnaire and Exit Survey								X	
Suicide Assessment (C-SSRS)		X		X	X	X		X	
Edinburgh Handedness Inventory – short form	X								
Blood collection for iPSC Lines				X 	(X  )	(X  )			
Neurophysiological Testing (TMS/NCS)	X	X			X	X			
Ophthalmologic Examination 		X						X	
Lumbar Puncture (Optional)					X 				
Pharmacokinetics (PK)/Biobanking					X				
Telephone Call 			X				X		X
Randomization 		X							
Administer/Dispense Study Drug		X 		X					
Drug Accountability/ Compliance		X		X 	X 	X 		X 	
Review of Muscle Symptoms Diary 		X		X	X	X		X	
Fasciculation Assessment Form		X		X	X	X		X	

 All clinic visits after the Baseline Visit will have a +/- 3 day window.

 Screening procedures must be completed prior to the Baseline Visit, which will be scheduled up to 21 days after the Screening Visit.

 Study staff should document the time the last dose of ezogabine was administered.

 Adverse events that occur AFTER signing the informed consent form will be recorded.

 Vital signs include systolic and diastolic pressure in mm Hg, respiratory rate/minute, heart rate/minute and temperature.

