## **4 STUDY DESIGN**

### **4.1 Overall Study Design and Plan**

During the enrollment period, approximately 150 ALS patients will be screened from approximately 12 Northeast ALS Consortium (NEALS) centers in the US. Approximately 120 eligible ALS subjects will be randomly assigned in a 1:1:1 ratio to oral ezogabine 600 mg/day, 900 mg/day or matching placebo. After randomization, subjects will undergo the Baseline Visit and take their first dose of study drug in clinic at that visit. All visit windows are consecutive calendar days and are calculated from the day the participant has their Baseline Visit (Day 0). An interim futility analysis will be performed after the first 45 ALS subjects have completed Week 12 of the study. One or the other active treatment groups or the full trial may be terminated based on results of the futility analysis and/or periodic review of safety data by the DSMB.

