## 8 STUDY SCHEDULE (ALS SUBJECTS)

No study procedures should be performed prior to the signing of the ICF. All subjects will sign an ICF prior to undergoing any study tests or procedures. The slow vital capacity (SVC) should be performed first at the visits so as not to fatigue the subject with other testing; however, the order of testing will be at the discretion of each site investigator (SI).

Visit windows are consecutive calendar days and the target visit dates are calculated from the Baseline Visit, which should occur within 21 days of the Screening Visit. All clinic visits and calls after the Baseline visit will have a +/- 3 day window, except the Week 14 phone call which has a +5 day window only.

Subjects who withdraw consent or terminate from the study early will be asked to come in for a Final Safety Visit within 14 days of withdrawing consent, and will have a Final Telephone Call no sooner than 28 days after last known dose of study drug.

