## 8.6 Week 8 Visit

This visit will take place  $56 \pm 3$  days after the Baseline Visit (after four weeks of maintenance drug dose). The following procedures will be performed:

- Review and document concomitant medications and therapies
- Assess and document AEs
- Measure vital signs including weight
- Collect blood samples and urinalysis for safety clinical laboratory assessments
- Administer ALSFRS-R questionnaire
- Administer the American Urological Association (AUA) Symptom Score survey
- Perform SVC
- Perform hand held dynamometry (HHD - APB bilaterally)
- Administer the suicide prevention (C-SSRS) questionnaire
- Perform neurophysiological testing (TMS and NCS)
- Check study drug compliance and dosing diary
- Review Muscle Symptom Diary with subject
- Complete Fasciculation Assessment
- Schedule next visit

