## **8.7 Week 12 Visit**

This visit will take place  $84 \pm 3$  days after the Baseline Visit (two weeks after drug cessation). The following procedures will be performed:

- Review and document concomitant medications and therapies
- Assess and document AEs
- Perform physical examination
- Perform neurological examination, including MMT
- Perform ophthalmologic examination (may be scheduled separately, but within 14 days of Week 12 Visit)
- Measure vital signs including weight
- Perform 12-lead ECG
- Collect blood samples and urinalysis for safety clinical laboratory assessments
- Administer ALSFRS-R questionnaire
- Administer the American Urological Association (AUA) Symptom Score survey
- Perform hand held dynamometry (HHD - APB bilaterally)
- Perform SVC
- Administer the suicide prevention (C-SSRS) questionnaire
- Check study drug compliance and collect dosing diary
- Review returned Muscle Symptom Diary
- Complete Fasciculation Assessment
- Perform study drug accountability and collect all unused study drug and empty containers
- Schedule telephone call
- Complete Blindedness Questionnaire and Exit Survey

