## **2.6 Treatment Administration**

Study drug will be orally self-administered in film-coated immediate-release tablets of a variety of strengths of ezogabine or matching placebo. In the 600 mg/day arm, ezogabine is titrated as follows: 100 mg TID for week 1, 150 mg TID for week 2, 200 mg TID for weeks 3 through 8, 200 mg BID for week 9, and 200 mg QD for week 10. In the 900 mg/day arm, ezogabine is titrated as follows: 100 mg TID for week 1, 150 mg TID for week 2, 200 mg TID for week 3, 250 mg TID for week 4, 300 mg TID for weeks 5 through 8, 200 mg BID for week 9, and 200 mg QD for week 10. In the placebo arm, participants receive a matching pseudo-titration of placebo tablets matched for size, color, and presentation.

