## 3.2 Study Endpoints

### 3.2.1 Efficacy Endpoints

The primary efficacy endpoint is the change from pre-treatment to the average of the week 6 and week 8 visits in paired-pulse short-interval intracortical inhibition (SICI) assessed by TMS.

The key secondary efficacy endpoint is the change from pre-treatment to the average of the week 6 and week 8 visits in resting motor evoked potential (MEP) threshold (RMT) assessed by TMS.

The other secondary efficacy endpoints are the change from pre-treatment to the average of the week 6 and week 8 visits in the following measures.

TMS measures:

- MEP amplitude at 120% of RMT,
- Intracortical facilitation (ICF), and
- Cortical silent period (CSP).

TTNCS measures:

- Strength duration time-constant (SDTC),
- Depolarizing and hyperpolarizing electrotonus at 90 to 100 ms (TEd(90-100 ms) and TEh(90-100 ms)),
- Recovery cycle measures of relative refractory period (RRP), superexcitability, and subexcitability, and
- Compound motor action potential (CMAP).

Clinical measures:

- ALS Functional Rating Scale-Revised (ALSFRS-R) total score,
- Slow vital capacity (SVC),
- Abductor pollicis brevis (APB) muscle strength by hand-held dynamometry (HHD),
- Muscle cramping frequency and pain, and
- Fasciculation occurrence and interference with daily life.

Exploratory efficacy measures include: maximum amplitude, minimum amplitude, midpoint of activation, and slope at the midpoint of activation from input/output curves; rheobase, TEd(40-60 ms), TEh(10-20 ms), TEd(peak), subexcitability after second pre-pulse, and stimulus for 50% maximum response assessed by TTNCS; MEP amplitude at 120% of RMT divided by CMAP.

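### The Week 8 TMS/NCS window (Day 56 ± 3) overlaps the Week 9 step from three to two daily doses, so some Week 8 SICI and RMT values can be taken on a one-third lower daily dose

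*Protocol*

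**What the plan says.** **Dosing.** Participants are randomized and then, at the Baseline Visit (Day 0), "take their first dose of study drug in clinic at that visit" (Protocol 4.1). Protocol 6.3 ties the number of tablets to the week of the study. In Table 1 both tablet strengths are taken TID in Weeks 5 to 8, BID in Week 9 and QD in Week 10. SAP 2.6 gives the same pattern for the 600 mg/day arm: "200 mg TID for weeks 3 through 8, 200 mg BID for week 9, and 200 mg QD for week 10". The kit for Weeks 5 to 10 is dispensed at the Week 4 Visit, which is itself Day 28 ± 3 (Protocol 6.3, 8.4).

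**Visits.** Protocol 8 states: "All clinic visits and calls after the Baseline visit will have a +/- 3 day window", with an exception only for the Week 14 call. The Week 8 Visit, at Day 56, is described as "after four weeks of maintenance drug dose" (Protocol 8.6). The Week 12 Visit, at Day 84, is described as "two weeks after drug cessation" (Protocol 8.7).

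**Endpoints.** Protocol 13.3 tests the "change from baseline to the average SICI over the stable dose period from weeks 6 through 8". SAP 3.2.1 defines both the primary endpoint (SICI) and the key secondary endpoint (RMT) as change from pre-treatment to the mean of the Week 6 and Week 8 values.

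**Dose timing.** A footnote to the ALS Schedule of Activities, attached to Weeks 4, 6 and 8, reads: "Study staff should document the time the last dose of ezogabine was administered". No analysis in the SAP uses that time.

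**The concern.** The endpoint is meant to capture response at the full maintenance dose. The Week 8 window extends past the day on which the schedule lowers that dose, and nothing in the Protocol or SAP requires testing to come first or the taper to wait. The reminder calls fall at Weeks 2, 10 and 14, so none is placed at this step.

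Because the overlap arises when the plan is followed exactly, deviation reporting would not reveal it. The analysis samples would not isolate it either. The mITT sample keeps these values. The per-protocol sample removes only observations after premature permanent discontinuation (SAP 3.5). None of the secondary analyses in SAP 3.8.2 separates them.

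At stake is some dilution of the active-versus-placebo difference in SICI and RMT. The trial is meant to inform a decision on a larger study (Protocol 3.1), so an understated pharmacodynamic effect matters, even though the error is on the cautious side.

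**Working it through.** **1. The plan's own power figure.** Inputs from Protocol 13.8 and SAP 3.4: 40 per arm, 25% loss, SD 30, difference 25, two-sided alpha 0.027, two-sample t-test. Evaluable per arm: 40 × 0.75 = 30. Noncentral-t power is 82.8%. The smallest evaluable number reaching 80% is 29 per arm (81.4%; 28 gives 79.8%), and 29/0.75 rounds up to 39, against 40 planned. The stated 80% is reproduced.

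**2. Calendar.**
- If Week 1 starts on Day 0, Weeks 5–8 are Days 28–55 and BID starts on Day 56. If it starts on Day 1, they are Days 29–56 and BID starts on Day 57. The descriptions of the Week 8 and Week 12 Visits fit this count.
- If Weeks 5–10 run from dispensing on Day 25 to 31, four weeks of TID put the step at about Day 53 to 59.
- The Week 8 window is Days 53–59. On the baseline count, Days 53–55 are on full dose, Days 57–59 are on BID by the latest start, and Day 56 depends on the count.
- The Week 6 window (Days 39–45) lies wholly within TID dosing.

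**3. Dose.** With the Protocol 6.3 kits, TID to BID is 600 to 400 mg/day in the lower arm and 900 to 600 mg/day in the upper arm, each a drop of one third. SAP 2.6 instead gives the upper arm 200 mg BID in Week 9 (400 mg/day). The kits cannot deliver that, because the 200 mg tablet is placebo in that arm. SAP 1 makes the Protocol authoritative on matters other than analysis, so one third is used.

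**4. Illustrative dilution.** Two quantities are assumed, because the documents give neither:
- *f*, the share of Week 8 tests after the changeover day. That is Days 57–59, or Days 58–59 if BID starts on Day 57. An even spread over the seven days gives 3/7 or 2/7. Visits peaked at Day 56 (weights 1-2-3-4-3-2-1) give 6/16 or 3/16.
- *L*, the loss of effect at those tests: one sixth to one third. One third is an immediate loss proportional to dose, and is near the upper end because only about 1 to 4 doses have been omitted by then.

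Week 8 has weight one half, so the diluted effect is 25 × (1 − f × L / 2). Power uses 30 per arm, SD 30, alpha 0.027.

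| f | L | Effect | Power |
|---|---|---|---|
| 0 | – | 25.00 | 82.8% |
| 3/16 | 1/6 | 24.61 | 81.5% |
| 3/16 | 1/3 | 24.22 | 80.2% |
| 6/16 | 1/6 | 24.22 | 80.2% |
| 6/16 | 1/3 | 23.44 | 77.3% |
| 2/7 | 1/6 | 24.40 | 80.8% |
| 2/7 | 1/3 | 23.81 | 78.7% |
| 3/7 | 1/6 | 24.11 | 79.8% |
| 3/7 | 1/3 | 23.21 | 76.5% |

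The two-visit mean keeps 98.4% to 92.9% of the effect.

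**5. Would the planned model show it?** SAP 3.8.1 fits a treatment effect at each post-baseline visit. The implied Week 8 minus Week 6 fade is 25 × f × L, or 0.8 to 3.6 points. Its standard error is 30 × √(2(1 − ρ)) × √(2/30). For an assumed Week 6–Week 8 correlation ρ of 0.5 this is 7.7, and for 0.7 it is 6.0. A fade of this size would be seen only imprecisely, and mixed with time.

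**The case against.** The calendar overlap is hard to dispute, but three objections carry weight.

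*The step date is inferred.* Neither document gives a study day for it, and counting from Week 4 dispensing moves it within about Day 53 to 59. This stands: the shares in the working are not anchored in the documents. Overlap remains possible on either count. The Manual of Procedures, which was not available, may already hold the taper until testing, in which case the effect is zero.

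*A lower daily dose is not the same as lower exposure at the test.* Each intake stays at 200 or 300 mg, and exposure during a session depends largely on time since the last intake, which also varies at Week 6. No half-life or concentration–response for SICI is given. In the upper arm, BID still delivers 600 mg/day, a dose that Protocol 2.2 regards as likely to reduce excitability. This stands too, and it makes the loss of one sixth to one third an assumption.

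*The effect is small even so.* With peaked visits and a one-sixth loss, power stays at 81.5% to 80.2%. The t-test is described in the plan as conservative relative to the mixed model. This bears on severity. It does not remove a dilution that the schedule allows and that costs little to prevent.

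A reader might go further and infer that Week 8 data as a whole are taken during the taper, with power near 66% (all Week 8 tests affected, one-third loss: effect 25 × 5/6 = 20.8). The documents do not support that: on the baseline count Days 53–55 are on full dose, and Day 56 at the earliest follows the complete maintenance period.

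**Conclusion.** The overlap is real and follows from the Protocol's own schedule: under full compliance, some Week 8 SICI and RMT values can be taken on a one-third lower daily dose, although Protocol 13.3 treats Weeks 6 to 8 as stable dosing. Any resulting bias is toward no effect and does not raise type I error. Its size cannot be determined from the documents. It is probably small: 82.8% power falling to about 81.5–76.5% under the assumed visit spreads and losses, on the planning scale rather than the log scale of the SAP analysis.

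It would be wrong to conclude that the primary analysis is invalid or the trial underpowered. Those readings need a visit-day distribution and a speed of response that neither document gives. Severity is minor to moderate, and the change is a cheap improvement.

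**What to change.** **Main change, for Week 8 visits still to come.** State in Table 1 and Protocol 8.6 that TID dosing continues until Week 8 TMS/NCS is done and that the BID step starts afterwards. On the baseline count, a hold of up to 3 days needs up to 3 × 1 = 3 extra tablets of each strength if the taper end date is kept, or up to 3 × 3 = 9 if the whole taper shifts. Kit overage is not stated and must be checked first; if dosing weeks run from Week 4 dispensing, the hold could be longer.

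**If supply does not allow this.** Require testing before the first omitted dose, for example a window of Day 56 −3/+0 with any Day 56 test done before that dose. This leaves 4 allowed days instead of 7. A −3/+0 window alone is not enough, because Day 56 may be the first BID day.

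Either change may reach few visits: SAP 3.7 places the final randomization less than three months after the 45th participant's complete follow-up.

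**Supplementary, before unblinding.** Keep the mITT primary analysis unchanged. In SAP 3.8.2, add a count per arm of Week 8 tests done after the first omitted dose, identified from the recorded last-dose time and the dosing diary, and one repeat of the SICI and RMT contrasts with those values set to missing. All arms follow the same tablet schedule, so the flag means the same in each.

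The variance ratio for the two-visit mean is [(1 − f)(1 + ρ)/2 + f] / [(1 + ρ)/2]. It rises by 6–14% at ρ = 0.5 and 3–8% at ρ = 0.7, so this is a low-precision check. Do not flag from the first scheduled taper dose: that would catch changeover-day tests before any dose was missed. With f as high as 4/7 or 10/16, the variance increase would then reach about 19–21% at ρ = 0.5 or 10–11% at ρ = 0.7. The dose-timing data are already collected.
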